4.2.2. Initial Dose Exploration (accelerated titration)

In order to minimize the number of subjects enrolled at sub-optimal doses, an accelerated titration design will be implemented until the first evidence of a non diseaserelated \geq Grade 2 toxicity, with the exception of toxicities listed in Section 4.2.4.2. One subject at each dose level will be enrolled, starting at the dose described in Section 4.7. If the subject enrolled at the first dose level experiences a dose-limiting toxicity (DLT), then lower doses (i.e., Dose Level -1) will be explored and re-escalation may be attempted based on safety and tolerability data. Accelerated titration will continue until a subject experiences a non-disease-related \geq Grade 2 toxicity, then the implementation of the MTD confirmation stage (Section 4.2.3) will be triggered. Each subject must complete the 21-day DLT evaluation period, and the available safety data must be reviewed before a decision is made on whether to proceed to the next dose level. If a subject fails to receive more than 80% of the planned doses within the 21-day DLT evaluation period for reasons other than toxicity, the subject will be replaced. Guidelines for selecting the next dose level are described in Section 4.2.4.2. Additional subjects may be enrolled at previously cleared dose levels if safety and PK analysis suggest this is warranted for better understanding the safety and PK profile. Safety assessments from these subjects will be included in the MTD determination.

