4.2.4.7. Intra-subject Dose Escalation

In Part 1, intra-subject dose escalations may be considered on a case-by-case basis, provided that the subject has completed at least the DLT observation period without

 \geq Grade 2 non disease-related toxicity in the first 21 days of therapy, that all subjects at the next highest dose level have completed the DLT observation period, and that prior approval has been obtained from the GSK Medical Monitor. Subjects may be dose-escalated to the highest cleared dose. Individual subjects may dose-escalate multiple times provided that the above criteria are met at each intra-subject dose escalation step. Safety assessments from these subjects will be included in the MTD determination.

Subjects approved for intra-subject dose escalation will initiate daily dosing from Day 1 of the higher dose (i.e., no dose interruption from Day 2 until Day 4) and will require additional PK sampling on Day 15 at the higher dose, as specified in Time and Events table (see Section 8.1). Additional safety assessments may be specified at the time of dose escalation or schedule modification based on the safety profile in previous subjects at the higher dose level. Intra-subject dose escalations or schedule modification will be discussed with investigators and approved by the GSK Medical Monitor and safety monitoring required will be specified in writing.

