11.10.2.1.2. Adverse Events

AEs will be coded using the standard MedDRA and grouped by system organ class. AEs will be graded by the investigator according to the NCI-CTCAE v4.

Events will be summarized by frequency and proportion of total subjects, by system organ class and preferred term. Separate summaries will be given for all AEs, treatment-related AEs, SAEs, and AEs leading to discontinuation of study treatment and dose modification. AEs, if listed in the NCI-CTCAE v 4, will be summarized by the maximum grade.

Dose-limiting toxicities will be listed for each subject and summarized by dose cohort for Part 1 subjects.

AEs of special interest will be outlined in the RAP.

The incidence of deaths and the primary cause of death will be summarized.

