5.1.1. Treatment Display

The actual treatment of a subject will be derived from exposure data. The first dose the subject received will be used as actual treatment. Scheduled (planned) treatment is collected on dosing regimen eCRF page. Efficacy, safety and PK analysis will be based on the All Treated Population.

Per Protocol Amendment 7, if the GSK3326595 tablet bioavailability is comparable to that of the GSK3326595 capsules from Part 1 Food Effect and Relative Bioavailability Sub-study, all new and ongoing subjects may be switched from capsules to tablets for the remainder of the study, once they have been notified by the Sponsor. As of 3 Nov 2021, per GSK communication, tablet and capsule cohorts within the same disease/dosage groups will be combined.

The leading dose formulation (tablet or capsule) and the leading dose level are specified in treatment.

- For Part 1 dose escalation cohorts, all data will be pooled and descriptive analyses summarized and listed by investigated GSK3326595 dose under QD dose escalation cohort or BID dose escalation cohort. PK/PD expansion cohorts will be summarized together with dose escalation cohorts dose level. If applicable, Part 1 Food Effect Relative Bioavailability Sub-study data will also be included in Part 1 summary tables as a separate column. The treatment groups for Part 1 are:
 - Part 1 QD Dose GSK3326595 12.5 mg Capsule
 - Part 1 QD Dose GSK3326595 25 mg Capsule
 - Part 1 QD Dose GSK3326595 50 mg Capsule
 - Part 1 QD Dose GSK3326595 100 mg Capsule
 - Part 1 QD Dose GSK3326595 200 mg Capsule
 - Part 1 QD Dose GSK3326595 300 mg Capsule
 - Part 1 QD Dose GSK3326595 400 mg Capsule
 - Part 1 QD Dose GSK3326595 600 mg Capsule
 - Part 1 BID Dose GSK3326595 50 mg Capsule
 - Part 1 BID Dose GSK3326595 100 mg Capsule
 - Part 1 BID Dose GSK3326595 150 mg Capsule
 - Part 1 BID Dose GSK3326595 200 mg Capsule
 - Food Effect and Relative Bioavailability Sub-study 300mg QD (apply to table/figures)
 - Part 1 Food Effect 300mg Sequence 1 (Tablet Fasted Tablet Fed Capsule Fasted) (apply to listings)
 - Part 1 Food Effect 300mg Sequence 2 (Tablet Fed Tablet Fasted Capsule Fasted) (apply to listings)
- For Part 2 dose expansion cohorts, data will be summarized and listed by cohorts. The treatment groups for Part 2 are:
 - Part 2 TNBC 400mg QD Capsule Cohort

- Part 2 mTCC 400mg QD Capsule Cohort
- Part 2 GBM 400mg QD Capsule Cohort
- Part 2 ER+BC 400mg QD Capsule Cohort
- Part 2 HPV+ 400mg QD Capsule Cohort

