3.57	All Treated	ODMOD1	Summary of Dose Reductions of GSK3326595	ICH E3 Part 1 (by dose), Part 2 (by cohort), Part 1/Part 2 300mg/400mg/Total/Overall, Part 3 (by dose)	SAC
3.58	All Treated	ODMOD1	Summary of Dose Reductions of Pembrolizumab	Part 3	SAC
3.59	All Treated	ODMOD2	Summary of Dose Interruptions of GSK3326595	ICH E3 Part 1 (by dose), Part 2 (by cohort), Part 1/Part 2 300mg/400mg/Total/Overall, Part 3 (by dose)	SAC
3.60	All Treated	ODMOD3	Summary of Dose Delays of Pembrolizumab	Part 3	SAC
3.65	All Treated	AE1	Summary of Adverse Events Recorded as Dose-Limiting Toxicities by Preferred Term– Part 1	ICH E3 Part 1	SAC
ECOG	Performance				
3.66	All Treated	PS1A	Summary of ECOG Performance Status	ICH E3 Part 1 (by dose), Part 2 (by cohort), Part 1/Part 2 300mg/400mg/Total/Overall, Part 3 (by dose)	SAC
Ocular	Adverse Event	s			
3.70	All Treated	from IB 2022	Summary of Adverse Events (Ocular Events) by Preferred Term	Part 1, Part 2, Part 3, Part 1+2	SAC
3.72	All Treated	from IB 2022	Summary of Adverse Events (Bone- Related Events) by Preferred Term	Part 1, Part 2, Part 3, Part 1+2	SAC
Bone N	Aineral Density	Shifts			

		IDSL / Example			
No.	Population	Shell	Title	Programming Notes	Deliverable
3.75	All Treated	from IB 2022	Summary of Bone Mineral Density Shifts from Baseline Relative to Normal Range, Among Patients with Pre- Treatment Baseline DEXA Scan – Local Labs	Part 1, Part 2, Part 3, Part 1+2	SAC
3.77	All Treated	from IB 2022	Summary of Bone Mineral Density Shifts from Baseline Relative to Normal Range, Among Patients with First DEXA Scan Performed on Treatment – Local Labs	Part 1, Part 2, Part 3, Part 1+2	SAC

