54	All Treated	TTE9	Listing of Progression-Free Survival Based on Investigator Assessment (Lugano Criteria)	Part 2 NHL cohorts	SAC
55	All Treated	custom per GSK	Listing of Time to Response Based on Investigator Assessment (RECIST 1.1 Criteria)	Part 2 ACC TN only	SAC
56	All Treated	TTE9	Listing of Overall Survival	Parts 2 and 3 by cohort	SAC

		IDSL /			
No.	Population	Example Shell	Title	Programming Notes	Deliverable
Adverse	e Events/Dose-L	imiting Toxicity			
61	All Treated	AE8	Listing of Adverse Events Recorded as	Part 1 (by dose)	SAC
			Dose-Limiting Toxicities		
Hepatol	piliary				
62	All Treated	LIVER5	Listing of Liver Monitoring/Stopping	Part 1 (by dose), Part 2 (by cohort), Part 3	SAC
			Event Reporting	(by dose)	
63	All Treated	LIVER15	Liver Stopping Event Profile	Part 1 (by dose), Part 2 (by cohort), Part 3	SAC
				(by dose)	
Troponi	n, ECG, and Vita	al Signs			
69	All Treated	OLB7	Listing of Local Troponin Data	Part 1 (by dose), Part 2 (by cohort), Part 3	SAC
				(by dose)	
70	All Treated	EG3	Listing of All ECG Values from Local	Part 1 (by dose), Part 2 (by cohort), Part 3	SAC
			Labs	(by dose)	
72	All Treated	VS5	Listing of All Vital Signs for Subjects	Part 1 (by dose), Part 2 (by cohort), Part 3	SAC
			with any Value of Potential Clinical	(by dose) List all VS data for any subject	
			Importance	with at least one PCI	
Other S	afety				
74	All Treated	DD3	Subject Profile for Death	ICH E3	SAC
76	All Treated	Custom	Listing of DEXA Bone Densitometry	Part 1 (by dose), Part 2 (by cohort), Part 3	SAC
			Data from Local Labs	(by dose)	
77	All Treated	Custom	Listing of Optical Coherence	Part 1 (by dose), Part 2 (by cohort), Part 3	SAC
			Tomography Results	(by dose)	
78	All Treated	Custom	Listing of Best Corrected Visual Acuity	Part 1 (by dose), Part 2 (by cohort), Part 3	SAC
			(Snellen Acuity Equivalent) Results	(by dose)	
PK					
79	PK	PK07	Listing of GSK3326595 Plasma	IDSL List all data Part 1 (by dose), Part 2	SAC
			Pharmacokinetic Concentration-Time	(by cohort), Part 3 (by dose). Create	
			Data	another listing for Part 3 for Pembrolizumab	

		IDSL /			
No.	Population	Example Shell	Title	Programming Notes	Deliverable
80	PK	PK09	Listing of GSK3326595 Urine Sample	IDSL List all data Part 1 (by dose)	SAC
			Collections		
81	PK	PK11	Listing of GSK3326595 Urine	IDSL List all data Part 1 (by dose)	SAC
			Excretion Rate Data		
82	PK	PK13	Listing of Derived GSK3326595	IDSL List only D1, D15 Part 1 (by dose),	SAC

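### SAP 5.1.1 groups Part 1 subjects by first dose received, so a DLT judged to occur after intra-subject escalation would be tabulated under the lower starting dose

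*Protocol*

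**What the plan says.** **Escalation.** Protocol 4.2.4.7 allows a Part 1 subject to be escalated case by case, up to the highest cleared dose. The subject must have finished the DLT observation period without Grade 2 or higher non-disease-related toxicity in the first 21 days, and the Medical Monitor must approve. More than one step is possible: "Individual subjects may dose-escalate multiple times provided that the above criteria are met at each intra-subject dose escalation step". On use of the data it says: "Safety assessments from these subjects will be included in the MTD determination".

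**What counts as a DLT.** Protocol 4.2.4.1 ties DLTs to the first 21 days of treatment. Table 1 adds one later route: a Grade 2 or higher event after day 21 that the investigator and the Medical Monitor judge to be a DLT.

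**How subjects are grouped.** SAP 5.1.1: "The first dose the subject received will be used as actual treatment". For Part 1 it plans "descriptive analyses summarized and listed by investigated GSK3326595 dose under QD dose escalation cohort or BID dose escalation cohort". SAP 15.5.2 applies actual treatment to all reporting unless stated otherwise. SAP 15.6.2 lets actual treatment differ from assigned treatment only when the subject was on the different treatment throughout.

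**DLT displays.** Protocol 11.10.2.1.2: "Dose-limiting toxicities will be listed for each subject and summarized by dose cohort for Part 1 subjects". The SAP has Table 3.65, "Summary of Adverse Events Recorded as Dose-Limiting Toxicities by Preferred Term", whose programming note says only Part 1. It also has Listing 61, whose title begins "Listing of Adverse Events Recorded as" and which is by dose.

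**The concern.** DLTs are a primary endpoint of Part 1, and a DLT table exists to link toxicity to dose. Grouping by first dose is a common convention for general adverse event tables. For a subject whose dose was raised it breaks that link. The event is charged to a dose at which the subject had already passed the observation period, and it is missing from the dose being taken when it arose. Both cells are then wrong, in opposite directions.

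The cells can be small. In accelerated titration, "One subject at each dose level will be enrolled", and later cohorts are recruited in blocks of three. What is at stake is the reported DLT-by-dose summary and any statement in the study report that rests on it. No past dose decision is at stake.

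**Working it through.** The plan has no figure of its own on this point, so the check follows one subject through the rules and then does the cell arithmetic.

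**Tracing a subject (illustrative; the doses are planned levels in Protocol 4.2.4.4).** A subject starts at 50 mg QD, completes 21 days without a disqualifying toxicity, and is escalated to 100 mg and later to 200 mg. An event then occurs at 200 mg.

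1. *Can it be a DLT?* The 21-day window runs from the start of treatment and has closed. Protocol 4.2.4.7 states no new window at the higher dose. The event is a DLT only if it is Grade 2 or higher and judged dose-limiting under the late-event clause of Table 1.
2. *Which treatment group?* By SAP 5.1.1, the first dose received: 50 mg QD. SAP 15.6.2 does not move the subject, because 200 mg was not taken throughout.
3. *Which cell of the DLT summary?* Protocol 11.10.2.1.2 asks for dose cohorts. Under SAP 5.1.1 the subject sits in the 50 mg group, so the 50 mg cell gains the DLT and the 200 mg cell does not show it.
4. *Does any display use dose at onset?* No DLT display in SAP 8.1.1.2 or SAP 15.12 is described that way. Exposure (Listing 8), all adverse events (Listing 10) and DLTs (Listing 61) together would let a reader reconstruct it subject by subject.

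**If Table 3.65 is not by dose.** Its note leaves that open. In that case the misplacement does not arise in the table, but the by-cohort summary required by Protocol 11.10.2.1.2 is not delivered. Listing 61 would still place the subject under the starting dose.

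**Effect of one misplaced DLT on a starting-dose cell with no other DLT.** The change is (0 + 1)/n − 0/n = 1/n.

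| n at starting dose | Basis for n | Correct | As tabulated | Change |
|---|---|---|---|---|
| 1 | one subject per level, Protocol 4.2.2 | 0/1 | 1/1 | 100 points |
| 3 | blocks of three, Protocol 4.2.3 | 0/3 | 1/3 | 33.3 points |
| 12 | level expanded up to 12, Protocol 4.2.5 | 0/12 | 1/12 | 8.3 points |

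The n = 12 row matters because SAP 5.1.1 pools PK/PD expansion subjects with escalation subjects at the same dose. Protocol 4.2.2 also allows extra subjects at cleared levels, so a reported column need not have n = 1 or 3. At the dose of onset the event should appear over the number of subjects escalated to that dose, which the documents do not give.

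**The case against.** The case on the other side is substantial, and most of it limits the reach of the point.

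- *The route is narrow.* A post-escalation DLT needs prior approval to escalate and then a joint judgment that a late event was dose-limiting. The documents report no such event and no number of escalators. This stands.
- *Starting-dose grouping is a recognised convention, and the listings recover the facts.* Both true. The error is confined to how the event is presented by dose; the data are intact. The convention is a poor fit only for the DLT table.
- *The layout of Table 3.65 cannot be seen.* True. By-dose display follows from SAP 5.1.1 and Protocol 11.10.2.1.2, not from the table's own note.
- *A rule may exist elsewhere.* Protocol 4.2.4.5 refers to a Dose Escalation Plan and to written decisions, which are not available here. If they hold a counting rule, the report can state it.

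Two stronger readings are tempting and are not supported.

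First, Figure 4-1 shows E at 0/1 and 0/3, D at 1/1 and S at 1/3, so a reader might infer that a misplaced DLT would make a cleared dose fail the decision rule. It would not. Accelerated titration runs on the rules of Protocol 4.2.2, and mTPI starts only with the first cohort that shows a qualifying Grade 2 or higher toxicity. SAP Section 1 excepts the mTPI analysis from the work its authors carry out. The SAP tables do not feed Figure 4-1.

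Second, a reader might infer that including escalators biased the MTD. Protocol 4.2.4.7 does leave open whether they count at the old dose, the new dose or both, and Protocol 11.9.4 does not settle it. But neither the number of escalators nor their DLT rate is given. Selecting subjects without early toxicity could lower the rate at the higher dose, while longer exposure or the Grade 2 threshold for late events could raise it. Size and sign are both unknown. Protocol 4.3.2 bases the 400 mg RP2D on safety, tolerability, efficacy, PK and PD together, and Protocol 4.2.4.8 says an MTD may not need to be identified.

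**Conclusion.** The point holds as a fault in a stated reporting rule. Read with Protocol 11.10.2.1.2, SAP 5.1.1 places a DLT judged to occur after escalation under the starting dose and leaves the dose at onset without it. Each such event moves the starting-dose rate by 1/n, from 100 points at n = 1 to 8.3 points at n = 12.

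This assumes that at least one subject escalated, that at least one late event after escalation was judged a DLT, and that the DLT summary is shown by dose. The documents confirm neither of the first two. If neither happened, one sentence in the report closes the matter. The missing counting rule in Protocol 4.2.4.7 concerns decisions already taken. It calls for disclosure and gives no ground for saying the MTD or RP2D is wrong.

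**What to change.** In the Part 1 DLT summary (Table 3.65):

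1. Present the table by dose.
2. Main row: n by starting dose, as SAP 5.1.1 already gives it, counting only DLTs that occurred before any escalation. Keep judged DLTs beyond 21 days if the subject was still at the starting dose.
3. Separate supportive row: post-escalation DLTs by dose at onset, with the number of subjects escalated to that dose as denominator. A subject who escalated more than once enters the denominator at each dose reached.
4. One sentence stating how many subjects escalated and whether they were included in the mTPI counts.

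Escalators' safety data stay in the MTD assessment, as Protocol 4.2.4.7 requires, but are shown apart.

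The cost is small: a before/after-escalation flag on the DLT records, one row and one sentence. SAP 6.8 names the number of dose escalations as an example of an exposure summary, but no planned table title or note provides for it, so the count would come from the exposure records behind Listing 8. The drawback is a split table with few subjects in the supportive row. No past dose decision is reopened.

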4.2.4.8. Completion of Dose Escalation and Determination of MTD/RP2D

The dose escalation portion of Part 1 is expected to be completed when approximately 42 subjects enrolled in the dose escalation and dose confirmation stages have completed the DLT evaluation period. The RP2D will be the MTD or a lower dose that provides adequate PK exposure and biologic activity with superior tolerability. The identification of MTD may not be necessary if a clear RP2D emerges without reaching the MTD. The final determination of RP2D will be based on the mTPI suggested dose level, or the biologically active dose (e.g., clinical response), the safety profile, and available PK and PD data generated from all subjects in Part 1. If necessary, alternate schedules can be explored to determine additional biologically active doses even after a RP2D is defined.

Subjects may be enrolled at previously completed dose levels for the purpose of obtaining additional safety, PK, PD, metabolite, or biomarker data. Paired fresh biopsies (pre- and post-dose) may be required in these subjects based on the need to obtain tumor PD data. In addition, a reduced PK schedule may be used in subjects enrolled to obtain additional PK/PD data.

4.2.5. PK/PD, Metabolite, and Biomarker Expansion Cohort(s)

Any dose level at or near the MTD/RP2D in Part 1 may be expanded up to 12 subjects in order to collect additional data on safety and pharmacokinetics (PK). More than one dose level may be selected for expansion (e.g., to establish a dose-response curve for PD or other biomarkers), based on emerging data. Clinical samples from this/these cohort(s) will also be collected for analysis of pharmacodynamics (PD), metabolite profiling, and biomarkers. Subjects may be enrolled into this cohort even after MTD/RP2D has been identified and Part 2 of the study (Section 4.3) has been initiated.

Refer to Section 8.1, Time and Events Table (Table 10), which highlights the additional sampling requirements for this cohort. In addition to the safety and PK evaluations necessary for all subjects in Part 1, blood and urine will be collected at time points specified in Section 8.1 (Table 10) for PD, biomarker, and metabolite profiling. Pre-dose

and post-dose tumor biopsies will be required from subjects in this/these cohort(s). Subjects consenting to pre- and post-dose biopsies will be prioritized to enrollment in these cohorts. ¹⁸fluorodeoxyglucose (FDG) positron emission tomography (PET) (FDG-PET)/computed tomography (CT) scan (PET/CT scan) will be required for all subjects in this cohort, as described in Section 8.6.3.

4.2.6. Food Effect and Relative Bioavailability Sub-Study

Part 1 will include a sub-study that will be an open-label, randomized, single dose, three period, cross over study to investigate the effect of a high-fat, high-calorie meal on the bioavailability of GSK3326595, and compare two formulations of GSK3326595 (capsule versus tablet). The dose of GSK3326595 will be 300 mg once a day (QD) (refer to Section 4.3.2). GSK3326595 dosing will be separated by at least 48 hours between each period. Up to 12 subjects in the United States may be enrolled in the sub-study. A subject requiring dose reduction or discontinuation from study before completion of the sub-study will be replaced by a new subject. Depending on the data from the initial 12 subjects, up to an additional 12 patients may be enrolled in this sub-study. All subjects enrolled to the sub-study, on completion of their participation in this segment of the study, will continue on a daily dosing schedule until discontinuation criteria are met, as described in Section 5.4. Further details will be provided in the SRM. The sub-study will be open to adults, with histologically- or cytologically-confirmed solid malignancies as described for Part 1 in Section 5.1.

The high-fat (approximately 50% of the total caloric content of the meal), high-calorie meal (approximately 800 to 1000 calories) will be the representative example given by the 2002 US Food and Drug Administration (FDA) guidance [FDA, 2002]. Additional details of the required meal will be provided in the SRM.

Subjects enrolled in the sub-study will be assigned to one of two sequences, as described in Table 2; equal numbers will be assigned to each sequence. The schedule of visits for subjects enrolled in the sub-study is detailed in Table 13 in Section 8.1. Upon completion of the sub-study, all subjects will continue to undergo scheduled assessments as described in Table 9. Additional details, including the process of sequence assignment, will be provided in the SRM.

Table 2	Food Effect and Relative	Bioavailability Sub-Study
---------	--------------------------	----------------------------------

Food-Effect Sub-Study: Single Dose Administrations									
Sample Size	Sequence	Period 1 (D1)	Period 2 (D4)	Period 3 (D8)					
6	1	Fasted / tablet	Fed / tablet	Fasted / capsule					
6	2	Fed / tablet	Fasted / tablet	Fasted / capsule					

Fasted: Subjects should take nothing by mouth apart from water and other medications for at least 8 hours before drug administration and should continue fasting until at least 4

hours after administration of the morning dose. Subjects should be administered the drug product as a capsule or tablet (as indicated) with 200 mL (8 fluid ounces) of water. Water can be allowed, as desired, except for one hour before and after drug administration. All subjects will receive standardized meals at approximately 4- and 9- hours post dose. Additional details of the meals will be provided in the SRM.

Fed: Following an overnight fast (at least 8 hours), subjects should start the recommended high fat, high calorie breakfast 30 minutes prior to administration of the GSK3326595. Study subjects should eat this meal in 30 minutes or less; however, GSK3326595 should be administered 30 minutes after start of the meal. The GSK3326595 should be administered as a tablet with 200 mL (8 fluid ounces) of water. No food should be allowed for at least 2 hours post-dose. Water can be allowed, as desired, except for one hour before and after drug administration. All subjects will receive standardized meals at approximately 4- and 9- hours post dose. Further details of the meals will be provided in the SRM.

Any subject who experiences vomiting within 3 hours of dosing will be removed from the statistical analysis of PK comparability between tablet/capsule and tablet (fasted)/tablet (fed), and additional subjects will be enrolled to ensure 12 subjects complete all three periods.

As described in Section 8.2.2, the Day 4 (Period 2) visit may be performed on Day 4 or Day 5. The Day 8 (Period 3) visit (capsule administered in a fasting state) may be performed ± 1 day. Continuous daily dosing with GSK3326595 will only commence once the subject has completed the Period 3 visit, irrespective of whether that visit occurs ± 1 day.

If the GSK3326595 tablet bioavailability is comparable to that of the GSK3326595 capsules, all new and ongoing subjects may be switched from capsules to tablets for the remainder of the study, once they have been notified by the Sponsor.

